## **PROTOCOL OUTLINE AND GUIDELINES**

Investigators must submit well-organized, detailed information about the study, demonstrating sound research design that minimizes risks to the subject. PI should assure that the content outlined below is addressed and may exercise some discretion as to how the information is organized. The quality and content of the protocol should demonstrate that scientific and merit review of the study has occurred at the departmental level prior to submission to the IRB.

---

### **1. PROTOCOL INFORMATION**

Title: Efficacy of the liposomal bupivacaine for postoperative pain control in urologic procedures.

Phase of Study: Prospective Study. Phase IV

### **4. STUDY INFORMATION**

Location(s) of Research Activity: Loma Linda University Medical Center

Expected Start/Stop Dates of Research: 5-30-2016/5-30-2018

Special Time Sensitivities: None

Type of Research: Prospective randomized controlled study using patient information from medical records.

### **5. INCLUSION / EXCLUSION CRITERIA**

Inclusion criteria:

- Males or females 18-years-old or older.
- Undergoing urologic surgery.

Exclusion Criteria:

- Pregnant and/or nursing mothers.
- Allergy to bupivacaine.
- History of drug/alcohol abuse
- Severe cardiovascular, hepatic, renal disease or neurological impairment.

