### **6. SUBJECT RECRUITMENT & SCREENING**

Fifty subjects will be recruited for the study with an expected attrition rate of 10%. Sample size has been minimized, but is necessary for statistical power and

conclusions. Subjects will be male and female 18 years or older, of all ethnicities, denominations or other social/economical variations. All participants will speak English fluently in order for consent to be performed properly. Baseline pain score will be calculated through a questionnaire in at the urology clinic

Subjects of prospective study will be randomly divided using electronic program into two groups:

- The first group will receive intraoperative local Liposomal Bupivacaine injection at the port placement site.
- The control group will receive will local Marcaine (bupivacaine HCl) injection

Primary Outcome Measures:

- Total opioid consumption measured in intravenous morphine equivalents dose during the postoperative hospital Stay
- Postoperative pain assessment using visual Analog Pain Scores & Brief Pain Inventory form.
- Length of Hospital Stay
- Time to First Opioid Use.
- Postoperative Constipation , paralytic ileus

Time Frame: All data was recorded during the patient's hospital stay. All data will be collected from the electronic medical record, typically within 30 days of discharge from hospital.

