#### **9. DATA COLLECTION**

We will be using electronic medical records to retrieve data from subjects who will undergo urologic surgery and save it in a secured excel file.

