#### **11. DATA ANALYSIS**

We will compare the outcomes by comparing similar surgeries and in patients with similar epidemiology characteristics between who will receive liposomal bupivacaine injection to those who will receive (bupivacaine HCl) injection. It will focus on the pain related outcomes using SPSS.

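### Prescribed preoperative opioid use is neither recorded nor adjusted for, although opioid consumption and time to first opioid use are listed primary outcomes; the cost is lost precision, not systematic bias.

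*Combined protocol and SAP*

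**What the plan says.** Section 5 admits any adult having urologic surgery. Its nearest relevant exclusion is "History of drug/alcohol abuse". Prescribed opioid use without abuse is not mentioned.

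Section 6 gives five entries under primary outcomes, without ranking them. The first is "Total opioid consumption measured in intravenous morphine equivalents dose during the postoperative hospital Stay", and time to first opioid use is also on the list. A baseline pain score is to be taken in clinic; no other baseline measure is named. Patients are "randomly divided using electronic program into two groups", and neither section 6 nor section 7 names a stratification factor.

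Section 9 describes the data source: "We will be using electronic medical records to retrieve data from subjects". Section 11 says that similar surgeries will be compared, "in patients with similar epidemiology characteristics", using SPSS. It gives no model, test or covariate list.

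**The concern.** Opioid use before surgery is the natural baseline for how much opioid a patient takes after surgery and how soon. Existing users can be expected to have higher postoperative totals for reasons unrelated to the study drug. If their use is not in the analysis, that difference stays in the residual variance and widens the confidence interval for the treatment effect. In a trial of this size, one arm may also by chance contain several more users than the other, and an unadjusted comparison cannot take account of that.

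The wording in section 11 shows an intention to compare like with like, but it does not identify medication history. If the variable were added after the data had been seen, it could be criticised as post hoc selection. It therefore needs to be named in advance.

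**Working it through.** **Inputs from the documents.** 50 recruited and 10% attrition (section 6), so 50 × 0.90 = 45 evaluable. The allocation ratio is not stated; 1:1 is assumed, giving 23 and 22.

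**The plan's own figure.** Section 6 says only "Sample size has been minimized, but is necessary for statistical power and" conclusions. It states no alpha, power, difference or SD, so 50 can be neither confirmed nor refuted. Back-solving with 45 evaluable, two-sided 5% and a normal approximation, the detectable difference is (1.960 + 0.842) × √(2/22.5) = 0.835 SD at 80% power, and (1.960 + 1.282) × √(2/22.5) = 0.966 SD at 90%. A difference of 0.8 SD is used below for illustration.

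**Assumed inputs (not in the documents).** Prevalence of prior use p = 10–20%. Extra consumption in users k = 0.5–2 within-group SD. Normal residuals with SD 1. Prior use is the only covariate.

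**Variance and power.** With v = p(1−p)k², the variance share is R² = v/(1+v), the unadjusted SD is √(1+v), and adjusting 45 patients is worth 45/(1−R²) = 45(1+v) unadjusted patients. Power is for a two-sided 5% t-test, 23 vs 22, true difference 0.8.

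| p | k | v | R² | 45 adjusted worth | Power unadjusted | Power adjusted |
|---|---|---|---|---|---|---|
| 10% | 0.5 | 0.0225 | 2% | 46 | 74% | 75% |
| 10% | 1 | 0.09 | 8% | 49 | 71% | 75% |
| 10% | 2 | 0.36 | 26% | 61 | 61% | 75% |
| 20% | 0.5 | 0.04 | 4% | 47 | 73% | 75% |
| 20% | 1 | 0.16 | 14% | 52 | 68% | 75% |
| 20% | 2 | 0.64 | 39% | 74 | 54% | 75% |

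The gain runs from about 1 point (10%, 0.5 SD) to about 21 points (20%, 2 SD).

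**Chance imbalance.** The between-arm difference in the proportion of users has SD √[p(1−p)(1/23 + 1/22)], which is 0.089 at 10% and 0.119 at 20%. An imbalance of that size shifts the unadjusted difference by k times as much: 0.5 × 0.089 = 0.045 SD at the low corner and 2 × 0.119 = 0.24 SD at the high corner. The unadjusted standard error is √(1+v) × √(1/23 + 1/22), or 0.30 and 0.38 SD at the same corners. The shift is thus 0.15 to 0.62 of a standard error. This ratio equals √R² (√0.022 = 0.15, √0.39 = 0.62), so imbalance and extra variance are the same quantity seen two ways. By exact binomial sums, a gap of 10 percentage points or more between the arms has probability 21% at p = 10% and 37% at p = 20%.

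**Type I error.** Simulation of an unadjusted t-test under no treatment effect (22 vs 23, 40,000 trials per scenario, p = 20%) gave an overall error of 5.2% at k = 1 and 5.0% at k = 2. In the 19% of trials with an imbalance of 15 points or more, the error was 8.9% and 15.0% respectively.

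**The case against.** A reader might infer that chance imbalance in prior users could drive the trial's result. The documents do not support that. Patients are randomised, overall type I error stays near 5%, and the ordinary standard error already allows for a typical imbalance. The raised error rates apply only within unlucky allocations. A reader might also take opioid consumption to be the main outcome because it comes first; section 6 does not rank its list, and section 11 says only that the focus is on pain-related outcomes.

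Three further objections have force. First, the upper end of the range comes only from the 20%, 2 SD corner, and at 0.5 SD the gain is 1–2 points. Second, the figures credit prior use with its full marginal contribution. Pain score and surgery type may carry part of the same information, and a yes/no field mixes occasional with daily use; both would reduce the gain. Third, section 11 specifies no model at all, so this omission is one part of a wider gap, and the undefined reference to epidemiology characteristics cannot be proved to leave out opioid history.

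These points limit the size of the claim but do not remove it. Opioid history is not named anywhere, it is the closest baseline to two listed primary outcomes, and it can reasonably be expected in the record that is already being abstracted.

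**Conclusion.** The point holds as a loss of precision that is cheap to reduce. Prescribed preoperative opioid use is not excluded, not recorded as a baseline, not stratified on and not named as a covariate. On the assumed ranges, adjustment makes 45 evaluable patients worth about 46–74 and raises power for a 0.8 SD difference from about 54–74% to about 75%. These are illustrative figures for a sole covariate that is measured without error; the real gain depends on a prevalence and an effect that the documents do not give, and could be negligible. The finding does not show systematic bias or an inflated overall error rate, and it does not show that eligibility is wrong.

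**What to change.** In section 9, add one field to the record abstraction: any opioid on the medication list in the 30 days before surgery, yes or no. In section 11, prespecify it as a covariate in the regression for total opioid consumption, together with the clinic baseline pain score and a coarse grouping of surgery type. Leave eligibility unchanged.

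The cost is one extra chart field and a few model degrees of freedom. Surgery type needs a coarse grouping because section 5 admits any urologic operation and only about 45 patients will be evaluable. At 10–20% prevalence the opioid coefficient would rest on perhaps 5–9 users (45 × 0.10 = 4.5; 45 × 0.20 = 9), so it should serve as an adjustment term and not be interpreted in its own right.

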### **6. SUBJECT RECRUITMENT & SCREENING**

Fifty subjects will be recruited for the study with an expected attrition rate of 10%. Sample size has been minimized, but is necessary for statistical power and

conclusions. Subjects will be male and female 18 years or older, of all ethnicities, denominations or other social/economical variations. All participants will speak English fluently in order for consent to be performed properly. Baseline pain score will be calculated through a questionnaire in at the urology clinic

Subjects of prospective study will be randomly divided using electronic program into two groups:

- The first group will receive intraoperative local Liposomal Bupivacaine injection at the port placement site.
- The control group will receive will local Marcaine (bupivacaine HCl) injection

Primary Outcome Measures:

- Total opioid consumption measured in intravenous morphine equivalents dose during the postoperative hospital Stay
- Postoperative pain assessment using visual Analog Pain Scores & Brief Pain Inventory form.
- Length of Hospital Stay
- Time to First Opioid Use.
- Postoperative Constipation , paralytic ileus

Time Frame: All data was recorded during the patient's hospital stay. All data will be collected from the electronic medical record, typically within 30 days of discharge from hospital.

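### Section 11 gives the collected baseline pain score no use; an analysis of covariance on it, with surgery type as a fixed factor, is a cheap and conditional precision gain, not a bias correction

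*Combined protocol and SAP*

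**What the plan says.** Section 6 plans a preoperative measurement: "Baseline pain score will be calculated through a questionnaire in at the urology clinic". The questionnaire is not named. The same section lists, among five primary outcome items, "Postoperative pain assessment using visual Analog Pain Scores & Brief Pain Inventory form", without a time point or a choice of Brief Pain Inventory score.

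Section 11 is the only analysis text. Its basis for comparing the arms is "comparing similar surgeries and in patients with similar epidemiology characteristics", and it adds "It will focus on the pain related outcomes using SPSS". It gives no test, model or covariate list and does not mention the baseline score. No other section gives that score a use.

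Three other places bear on the point. Section 5 admits anyone "Undergoing urologic surgery". Section 7 has patients assigned by a code at the time of enrolment, and does not say whether the clinic score comes before or after. Section 9 describes data retrieval from electronic records only, so how a clinic questionnaire score reaches the dataset is not stated.

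**The concern.** A baseline measure of the outcome is usually the first candidate covariate in a small trial with a continuous endpoint. Here it is to be collected and then has no stated role. What section 11 offers instead has no defined form: similar surgeries could mean matching, subgroups or a model factor, and the epidemiological characteristics are not listed. They might or might not include baseline pain. Matching or subgrouping would also risk leaving randomised patients out of the comparison.

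The stake is precision. With about 45 evaluable patients only a large difference is detectable, so a covariate already planned for collection is worth using if it predicts postoperative pain.

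**Working it through.** **Inputs from the documents.** 50 patients recruited and 10% attrition (section 6), so 50 x 0.9 = 45 evaluable. The plan's own figure of 50 cannot be reproduced: section 6 says only "Sample size has been minimized, but is necessary for statistical power and" conclusions, with no alpha, power, effect size or SD.

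**Assumed.** 1:1 allocation (23 v 22), two-sided 0.05, 80% power, effects in SD units, and a baseline-outcome correlation r (within arm and surgery type) between 0 and 0.5.

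**Step 1: plain comparison.** SE = sqrt(1/23 + 1/22) = 0.2982 SD. With 43 df and the noncentral t, the detectable difference is 0.855 SD.

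**Step 2: baseline pain as the only covariate.** The variance is multiplied by (1 - r^2) x (1 + 1/41), where the second factor is the average cost of estimating the slope; df = 42. At r = 0.3: 0.91 x 1.0244 = 0.9322, SE = 0.2982 x sqrt(0.9322) = 0.2879, detectable difference 0.826 SD, and 0.826/0.855 = 0.966. The interval widths and shares below are simulated, 15,000 trials per r.

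| r | Detectable difference (SD) | Mean CI width v plain | Trials with a narrower CI |
|---|---|---|---|
| 0 | 0.866 | +1.3% | 20% |
| 0.2 | 0.848 | -0.8% | 49% |
| 0.3 | 0.826 | -3.4% | 73% |
| 0.5 | 0.750 | -12% | 97% |

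Break-even is near r = 0.16. These are averages: at r = 0, chance imbalance raises the SE by 3.2% at the 90th percentile and 4.6% at the 95th.

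**Step 3: baseline pain added to a model that already has surgery type.** With 3 to 5 equal-sized categories the increment is almost the same: +1.3 to +1.4% at r = 0, -3.2 to -3.4% at 0.3, -12% at 0.5.

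**Step 4: the recommended model, baseline pain plus three surgery categories, against the plain comparison.** If neither term predicts pain, the simulated ratio of mean CI widths is 1.039. The closed form agrees: sqrt(42/39) = 1.038 for three covariate df, times 1.002 for the larger critical value. Predictive value multiplies this by sqrt((1 - r^2)(1 - S)), where S is the share of variance explained by surgery type.

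- Break-even with S = 0: r^2 = 1 - 1/1.039^2 = 0.074, so r = 0.27.
- r = 0.3, S = 0: 1.039 x sqrt(0.91) = 0.991, or -0.9%.
- r = 0.3, S = 0.20: 1.039 x sqrt(0.91 x 0.80) = 0.887, or about -11%.

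More categories cost more. If neither term predicts pain, four give +5.3% and five give +6.7%.

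**Step 5: is there bias to correct?** Simulated with N = 45, a true difference of 0.835 SD and r = 0.5, the unadjusted estimate averaged 0.834 and the adjusted one 0.835. The empirical SE fell from 0.298 to 0.261. Both are unbiased; only the spread changes.

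**The case against.** The strongest objection is that this is an optional efficiency choice. The unadjusted comparison is valid, the gain depends on a correlation found nowhere in the documents, and section 5 does not require preoperative pain, so r could be low. This stands as a limit on weight. It does not remove the point, because the similar-surgeries comparison is already promised and needs some defined form.

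A second objection is that the attractive figures belong to baseline pain alone. This is right: the two-term model needs r of about 0.27, not 0.16, to break even if surgery type is unrelated to pain. The 20% share for surgery type is also an assumption. Section 6 places the injection at port sites and section 8 at surgical or wound sites, passages that should be reconciled. If only port-based operations are meant, surgery type may explain less than assumed.

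A third objection is that the undefined epidemiological characteristics may already include baseline pain. They may, but the text does not say so.

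A reader might infer that ignoring baseline pain biases the trial, or that chance baseline imbalance invalidates the result. The documents do not support this: assignment is random, and the unadjusted confidence interval already allows for chance imbalance.

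**Conclusion.** The point holds as a precision improvement. The baseline score is collected and given no analytic use, and the comparison that section 11 does describe is undefined. Under the assumptions listed, the recommended model ranges from a 3.9% wider interval on average, if neither term predicts pain, to one about 11% narrower at r = 0.3 with 20% of variance due to surgery type. Neither r nor that share can be taken from the documents, so a gain is plausible but not assured.

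It would be too strong to say that the planned comparison is invalid, or that adjustment is certain to help. The change also does nothing for the unexplained sample size or the several primary outcomes, which are separate matters.

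**What to change.** In section 11, state that:

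- postoperative visual analogue and Brief Pain Inventory scores, with one summary and one time window each, fixed before data are seen, are compared between randomised arms by analysis of covariance, fitted separately to each score;
- the clinic baseline pain score is the covariate, and surgery type is a factor with at most three categories fixed before data are seen; this factor is the similar-surgeries comparison and replaces any matching or subgrouping;
- all randomised patients with a postoperative score stay in the model, and a missing baseline score is replaced by the overall baseline mean;
- the adjusted difference with its 95% confidence interval is the main result, and the unadjusted difference is also shown.

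Delete the epidemiological-characteristics wording, or replace it with a named list fixed in advance.

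In section 6, name the questionnaire score that serves as baseline, require that it be entered in the study dataset, and require that it be recorded before assignment is known. The last is needed because section 7 assigns patients at enrolment, and a self-reported score given after assignment is known could be influenced by it.

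The cost is a few sentences, the prior choice of time windows and surgery categories, and three degrees of freedom (one for baseline pain, two for surgery type). If neither term predicts pain, the interval is 3.9% wider on average, and more in some randomisations. If 10% of baseline scores are missing and mean-filled, the gain from baseline pain alone falls from 3.4% to 2.9% at r = 0.3, and from 12% to 11% at r = 0.5. The change covers these two pain scores only.

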## **7. INFORMED CONSENT PROCESS**

Informed consent will be accomplished and signed at the Urology offices in the LLUMC or at the Urology FMO clinic. Consent will be obtained by the research coordinator or other trained investigators. Subjects will be randomly assigned as they are enrolled using a code system.

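### Any urologic surgery is eligible and the analysis compares like operations, but allocation is not stratified by operation, so case-mix balance is left to chance

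*Combined protocol and SAP*

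**What the plan says.** **Eligibility.** Section 5 requires age 18 or over and "Undergoing urologic surgery". It gives no list of procedures and no restriction by surgical approach. Section 6 has the liposomal product injected where the ports are placed, which hints at port-based surgery. Section 8 speaks of injection at every wound, and of urologic operations in general. The scope is therefore ambiguous, and section 5, which governs entry, is broad.

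**Size.** "Fifty subjects will be recruited for the study with an expected attrition rate of 10" per cent (section 6).

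**Allocation.** Section 6: "Subjects of prospective study will be randomly divided using electronic program into two groups". Section 7: "Subjects will be randomly assigned as they are enrolled using a code system". This is all the protocol says about the method. It states no ratio, blocks, minimisation or stratification factor. Sections 6 to 8 describe no blinding.

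**Analysis.** Section 11: "We will compare the outcomes by comparing similar surgeries and in patients with similar epidemiology characteristics". No surgery categories, model or covariates are named.

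**The concern.** The analysis rests on comparing the two arms among patients who had like operations, but nothing in the allocation secures both arms, or balanced arms, within any class of operation. Type of operation plausibly drives opioid use, length of stay and ileus, all of which section 6 lists as primary outcomes. In a trial this small, a chance excess of larger operations in one arm would push these outcomes in the same direction, and the result could be mistaken for a treatment effect or could hide one. Allocation cannot be redone once patients are enrolled, so this has to be settled beforehand.

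**Working it through.** **Inputs.** Recruited: 50; attrition 10% (section 6); completers 50 × 0.90 = 45. The 50 itself cannot be reproduced, because section 6 gives no effect size, standard deviation, alpha or power; it says only "Sample size has been minimized, but is necessary for statistical power and" conclusions. *Assumptions:* simple 1:1 allocation (neither the method nor the ratio is stated) and the surgery mixes below (the protocol gives none).

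**1. Imbalance in a given set of operations.** Suppose eight of the patients have major operations. Under simple 1:1 allocation the number in one arm is binomial (8, ½):

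P(6:2 or worse) = 2 × (1 + 8 + 28)/256 = 74/256 = 0.289, or 29%.

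**2. Imbalance in a class holding 30% of patients.** With about 22.5 completers per arm, the standard deviation of the difference in proportions is √(0.30 × 0.70 × (1/22.5 + 1/22.5)) = 0.137. A gap of 0.20 is 0.20/0.137 = 1.46 standard deviations, with a two-sided tail of 0.14. Simulation with random arm sizes gives 0.146, so about 15%.

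**3. Narrow types with no comparator.** A type with m patients falls wholly in one arm with probability 2 × 0.5^m: 25% for m = 3 and 12.5% for m = 4. For a type with share p of 45 patients, the chance that it is present in one arm only is

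2 × [(1 − p/2)^45 − (1 − p)^45].

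This gives 0.5% at p = 0.25, 1.7% at p = 0.20, 18% at p = 0.10 and 44% at p = 0.05. The chance that at least one type is affected, by simulation with 45 patients, is:

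| Assumed mix | Simple 1:1 | Stratified by three broad classes, blocks of 2 and 4 |
|---|---|---|
| Four equal types | 2% | not run |
| Six types, 30/20/20/10/10/10% | 48% | 35–39% |
| Eight types, 30/20/10/10/10/10/5/5% | 87% | 80–82% |

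The ranges in the last column come from different ways of grouping the types into three classes. In the eight-type mix, the mean number of patients without a comparator falls only from about 3.5 to about 2.5. Forcing equal arm totals without stratifying changes little (45% for six types, 86% for eight).

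**4. Broad classes.** With only three classes, a class present in one arm only is already rare under simple allocation: about 0.2% for three equal classes and about 7% for a 60/25/15% split. For a class as small as 10%, the formula in step 3 gives 18%.

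**5. What stratification secures.** With blocks of at most 4 within a class, arm counts in that class differ by at most 2 at assignment. Eight patients forming one class could then split no worse than 5:3, so the 6:2 split in step 1 cannot occur. Attrition can disturb this afterwards.

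**The case against.** Four arguments can be made on the other side.

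- **Randomisation is valid without stratification.** This stands for the overall comparison, which simple randomisation leaves unbiased. The issue is precision and chance imbalance at about 45 completers, plus a section 11 comparison that is not a plain overall one.
- **The method is unspecified, which is not the same as unrestricted.** This stands in part. An electronic program and a code system could include blocking, and simple 1:1 allocation is an assumption here. But no stratification by operation is stated, and forcing equal arm totals does not balance operations within them.
- **Enrolment may in practice be port-based inpatient surgery.** The port wording in section 6 and outcomes tied to the hospital stay point that way. Section 5 sets no such limit and section 8 points the other way. If only a few common operations are enrolled, the problem of missing comparators largely disappears, though chance imbalance remains.
- **Covariate adjustment would do.** An overall comparison adjusted for surgery class would deal with much of the concern, but section 11 specifies none. It belongs in the fix.

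A reader might infer something stronger: that some surgery types will probably have no comparator, and that stratifying cures this. The protocol supports neither. The number and frequency of surgery types are not given, the chance runs from 2% to 87% over plausible mixes, and broad strata reduce it only partly. If broad classes are what section 11 means by similarity, a class with one arm empty is already uncommon, provided no class is very small.

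**Conclusion.** The point holds as one about chance case-mix imbalance. Eligibility is broad, the planned comparison depends on type of operation, and the stated allocation does not take it into account. Under simple 1:1 allocation with about 45 completers, a 6:2 or worse split of eight major operations has a 29% chance, and a gap of more than 20 points in a class holding 30% of patients has about a 15% chance. How far such a gap would shift the outcomes cannot be calculated, because the protocol gives no outcome figures by operation; that operation type matters for opioid use, length of stay and ileus is a reasonable assumption. The trial is not invalid without the change, but a cheap protection is being left out. Confidence is medium, because the allocation method, the ratio and the surgery mix are not stated.

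**What to change.** **Section 6.** State that the electronic program randomises 1:1 in permuted blocks of varying size (for example 2 and 4), stratified by booked operation in two or three broad classes fixed before enrolment, such as laparoscopic or robotic, open abdominal or flank, and other incisional. Choose classes that are each expected to hold a fair share of patients. Reconcile the descriptions of eligible surgery and injection site in sections 5, 6 and 8, so that the classes cover what will actually be enrolled.

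**Section 11.** Replace the comparison within like operations by one overall treatment comparison of all randomised patients, adjusted for those same classes.

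**Cost.** A new randomisation list in the program already planned and a few sentences of text, with no extra patients. There are two downsides. The operation class must be entered before assignment. Small blocks within strata also make some assignments predictable where staff are not blinded, and no blinding is described, so block sizes should vary and be withheld from enrolling staff. Stratification does not enlarge small classes, so comparisons within narrow surgery types should not be promised.

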## **8. STUDY DESIGN**

Background or rationale for this study:

Liposomal bupivacaine was developed to extend the duration of efficacy of bupivacaine from the typical 6 - 8 hours up to 72 hours. The prolonged duration of liposomal bupivacaine was initially demonstrated in mice in 1994. Two randomized controlled trials using liposomal bupivacaine for bunionectomy and hemorhoidectomy resulted in FDA approval for its use in humans. More recently, liposomal bupivacaine has also been found to improve pain control for patients undergoing total knee arthroplasty. Infiltration of a local anesthetic into laparoscopic port sites is a common practice that has been shown in some studies to improve postoperative pain. Currently, no standard of care exists for postoperative pain and management is based on surgeon and anesthesiologist preferences. Liposomal bupivacaine has been one form of administered local, long-acting analgesia that

surgical centers have turned to. In addition, the analgesia has fewer adverse effects than opioids, with comparable adverse effects to those seen in bupivacaine alone.

Objectives: A prospective, randomized controlled study to determine the efficacy of liposomal bupivacaine given by local injection at all the wound sites in patients undergoing urologic surgeries.

Procedures involved (Research Interventions):

- The first group will receive intraoperative local Liposomal Bupivacaine injection at the surgical site.
- The control group will receive and will receive local Marcaine (bupivacaine HCl) injection.

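### Five unranked bullets are all labelled primary, and the plan names no deciding outcome, alpha, success rule or multiplicity control

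*Combined protocol and SAP*

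**What the plan says.** The combined protocol and SAP puts five bullets under one heading in Section 6, "Primary Outcome Measures". In order, they cover:

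- the amount of opioid taken while in hospital, in morphine equivalents
- pain, on two instruments: "Postoperative pain assessment using visual Analog Pain Scores & Brief Pain Inventory form"
- how long the patient stays in hospital
- how long it takes until an opioid is first needed
- bowel outcomes, namely constipation and ileus

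The second and fifth bullets each hold two measures, so the count is seven if they are split. The bullets are not ranked.

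Section 8 states one objective, "to determine the efficacy of liposomal bupivacaine given by local injection at all the wound sites", and ties it to no outcome. Section 11 is the whole analysis plan. It describes a comparison between the two groups and adds "It will focus on the pain related outcomes using SPSS". It names no test, significance level, order of outcomes, success rule or adjustment, and no other section supplies them. On sample size, Section 6 says "Sample size has been minimized, but is necessary for statistical power", without an outcome, effect size, alpha or power value.

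**The concern.** An efficacy trial needs a rule, fixed beforehand, that turns its results into a yes or a no. Here several measures share the primary label and no such rule is given. A mixed result, such as lower opioid use with equal pain scores, would have no agreed reading. The plan would also leave open several routes to a positive claim, since whichever measure came out significant could be offered as the efficacy finding. If it were read that way, the chance of a false positive would exceed that of a single test. The sample-size sentence does not settle the matter, because it names no outcome for which the trial is powered.

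**Working it through.** **The plan's own figures.** No error rate is stated, so there is none to reproduce. The sample size of 50 cannot be rebuilt either, because no alpha, power, effect size or SD is given. The only available arithmetic is 50 × 0.90 = 45 evaluable patients after the 10% attrition in Section 6.

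**Inputs**

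- Number of measures, k (Section 6): 5 as bulleted, 7 if the two paired bullets are split.
- Pain-related subset: k = 4 (opioid total, visual analog score, Brief Pain Inventory, time to first opioid). This is a reading of Section 11, which does not list them.
- Assumed, because the document is silent: each measure is tested two-sided at 5%, so 2.5% in the direction favouring liposomal bupivacaine; any one significant result may be claimed; test statistics are normal with a common correlation ρ from 0.9 to 0.

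**Step 1: independence (ρ = 0), false claim favouring liposomal bupivacaine, 1 − 0.975^k**

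- k = 4: 1 − 0.975^4 = 0.0963
- k = 5: 1 − 0.975^5 = 0.1189
- k = 7: 1 − 0.975^7 = 0.1624

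**Step 2: common correlation ρ.** The rate is 1 − ∫ φ(t) · Φ((1.96 − √ρ·t)/√(1 − ρ))^k dt, by numerical integration.

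| k | ρ = 0.9 | ρ = 0.7 | ρ = 0.5 | ρ = 0 |
|---|---|---|---|---|
| 1 | 2.5% | 2.5% | 2.5% | 2.5% |
| 4 | 4.7% | 6.5% | 7.8% | 9.6% |
| 5 | 5.1% | 7.4% | 9.1% | 11.9% |
| 7 | 5.7% | 8.9% | 11.5% | 16.2% |

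Relative to one test, this is 0.0468/0.025 = 1.9 to 0.0963/0.025 = 3.9 times for four measures, and 0.0508/0.025 = 2.0 to 0.1189/0.025 = 4.8 times for five.

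**Step 3: bowel outcomes by Fisher's exact test.** This test is conservative in small samples. With 23 v 22 patients (1:1 allocation assumed), event rates of 5% to 50% assumed and all seven tests independent, the rate is 1 − 0.975^5 × (1 − f)^2, where f is the Fisher size in the favourable direction.

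- Liposomal bupivacaine in the arm of 23: f = 0.007 to 0.022, giving 13.1% to 15.7%.
- Liposomal bupivacaine in the arm of 22: f = 0.0016 to 0.018, giving 12.2% to 15.0%.

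The document does not say which arm would be larger, so the range is about 12% to 16%.

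**Step 4: power if several measures stay primary under Holm.** Take the case where only one measure is truly affected, with a two-sample t-test at 23 v 22 and every measure treated as normal. Power for that measure is approximately its power at 0.05/k.

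| True effect | One test at 0.05 | k = 4 | k = 5 | k = 7 |
|---|---|---|---|---|
| 0.855 SD | 80% | 60% | 57% | 52% |
| 0.7 SD | 63% | 41% | 38% | 33% |

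The loss depends on the effect size: for k = 4 it is 80 − 60 = 20 points at 0.855 SD and 63 − 41 = 22 points at 0.7 SD.

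**The case against.** **The inflation is conditional.** It arises only if any one significant result counts. If every measure had to succeed, there would be none, and the cost would be joint power instead. This stands. A reader might infer that the investigator intends to claim efficacy on whichever measure is significant. The document does not say so. It states no rule at all, and that silence is the defect.

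**Seven measures overstates the problem.** A reader might take 16% as the headline error rate. The document does not support that. The seven-way split is not the plan's own count, and 16.2% needs full independence among measures that plainly overlap. Section 12 lists constipation among the common adverse reactions to the study drug, Section 13 names only less pain and a shorter stay as benefits to the patient, and Section 11 points to pain. A lone bowel difference is therefore a doubtful route to an efficacy claim. This stands too, so the four- and five-measure figures carry the point.

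**The range is not a bound.** Independence is the upper end only if correlations are not negative, which the document does not establish. In the other direction, Section 6 fixes no time point or summary score for the pain scales, so there could be more tests than counted. The figures are illustrations, neither floor nor ceiling.

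**The pain focus is a priority.** It is a partial one, and it deserves credit. It still leaves up to four measures with no order among them.

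**This is a 50-patient, single-centre Phase IV study.** That limits the consequences of an error, but not the need for a decision rule in a randomized trial whose stated aim is efficacy.

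**Conclusion.** The point holds as a missing decision rule: five bullets are labelled primary against one efficacy objective, and the plan gives nothing to say which decides, at what alpha, or by what rule. That much rests on the text alone.

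The size rests on assumptions: two-sided 5% per measure, any one result sufficient, and a common correlation of 0.9 to 0. Under these, a false claim favouring liposomal bupivacaine has a chance of 4.7% to 9.6% (four pain-related measures) or 5.1% to 11.9% (five bullets), against 2.5%. For seven measures the range is 5.7% to 16.2%, or about 12% to 16% at independence with Fisher's exact test on the bowel outcomes. Even with strong overlap and only the pain measures, the rate is nearly double that of one test. It should be fixed before outcome data are analysed, because a rule chosen afterwards would not be credible.

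**What to change.** Before any outcome data are analysed, the investigator names one primary outcome and states that it is tested at two-sided 5%. Total opioid use in morphine equivalents is one candidate; the choice is the investigator's. The rest become secondary, reported as estimates with 95% confidence intervals, or tested by Holm or in a stated fixed order.

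If several outcomes stay primary, the plan states whether one or all must succeed. Where one is enough, Holm is applied across them. Where all must succeed, no alpha split is needed, but joint power should be considered.

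The cost is protocol wording. With one named primary outcome, its own power is unchanged, but a lone positive secondary result can no longer be presented as the efficacy finding. Keeping several under Holm costs power when only one is truly affected, as the last table shows. Those power figures treat every measure as normal, which is a simplification for time to first opioid and the bowel outcomes, and for opioid total and length of stay if these are skewed.
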